## **1.0 BACKGROUND**

Over the last decade, video-assisted thoracoscopic surgery (VATS) has become the standard of care for surgical resections of early stage lung cancers with proven benefit in terms of perioperative morbidity, length of stay and post-operative pain, while providing equivalent long-term and oncological outcomes when compared to conventional open surgery (1-5).

Enhanced recovery after surgery (ERAS) has been implemented in many surgical specialties and has shown positive outcomes. Key principles and concepts of ERAS include pre-operative counselling, nutrition optimization, standardized multimodal analgesia and early mobilization (6). Our institution has adopted enhanced recovery pathways (ERP) for a variety of surgical procedures, including esophageal and upper gastrointestinal surgeries, which led to shorter length of stay (LOS) and cost savings (7-9). For lung surgery, few studies have been published describing outcomes with ERPs (10, 11). Larger prospective trials are therefore needed.

A shorter LOS is an attractive concept with regards to hospital resource management, but moreover for improving patient factors such as recovery, function and quality of life. Our centre implemented an ERP for open and VATS lobectomy in 2012 which led to shorter LOS, lower complication rates, but no difference in readmissions or chest tube reinsertions (12). A cost analysis of this ERP was performed to evaluate the economic impact and revealed significantly reduced societal costs (average of \$4396 per patient) (13).

## **2.0 HYPOTHESIS**

For patients undergoing an uncomplicated VATS anatomical lung or wedge resection and enrolled in an ERP, same-day discharge is safe and feasible, and will not result in a higher rate of adverse events as compared to patients on a same-day admission pathway with an expected length of stay of 2 days.

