### **3.0 OBJECTIVES AND PURPOSE**

The aim of this phase I study is to evaluate the safety and feasibility of same-day discharge in participants undergoing anatomical lung resection (segmentectomy or lobectomy) or wedge resection by VATS with an ERP.

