#### **Feasibility of the Pilot Study**

This pilot study design will be deemed feasible for larger investigations if:

1. The sample population size can be achieved
2. Greater than fifty per cent (>50%) of consented participants are able to continue with same-day discharge post-operatively
3. There are no Serious Adverse Events (SAE) raising concerns about the safety of this ERP

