### **4.0 PARTICIPANTS**

This trial will be enrolling 20 participants from the Montreal General Hospital (MGH) at McGill University who are scheduled for an elective anatomical lung or wedge resection with suspected or confirmed pulmonary malignancy. When 20 participants are successfully consented the trial will close to accrual.

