### **5.0 DESIGN, METHODOLOGY AND ANALYSIS**

#### **5.1 Study Design**

- Study phase and type: Phase I, prospective observational pilot study
- Study blinding: Open-label
- Study allocation: N/A, single-arm study
- Study setting: Single center, Division of Upper Gastrointestinal and Thoracic Surgery at McGill University Health Centre (Montreal General Hospital)
- Research intervention: Enhanced recovery pathway (ERP) for VATS anatomical lung resection or wedge resection for same-day discharge from hospital
- Estimated enrolment period: September 2022 to September 2023
- Estimated duration of trial: Up to 1 year from first participant enrolled with verbal or signed informed consent to last study-related participant follow-up.
- Estimated duration of trial per participant involvement: From day of consent, to surgery, through follow-up within trial terms (for 4-6 weeks) for a total of approximately 2-3 months. Further follow-up according to usual treatment plan / lung cancer follow-up.

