## 5.4 Description of outcomes

### Primary Outcomes

1. Adverse event rate: Proportion of participants experiencing complications related to surgery (classified per type of complication).
2. Same-day discharge rate: Proportion of participants enrolled in the trial that go home on the day of the surgery.
3. Readmission rate: Proportion of participants requiring hospitalization due to complications or conditions related to the surgery.
4. Rate of presentation to the emergency room after surgery: Proportion of participants presenting to the emergency room due to complications or conditions related to surgery.

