## 5.5 Statistical analysis

Participants that meet criteria (inclusion and exclusion) will be prospectively enrolled into this trial. Clinical data will be prospectively collected according to the Thoracic Surgery Quality monitoring, Information management, and Clinical documentation (TSQIC) software data management system and subsequently extracted for analysis; <https://tsqic.org/tsqic/>. [See Appendix 4]

Demographic characteristics (sex, age), baseline characteristics (past medical and surgical history, smoking status, occupational exposure), diagnostic data (pulmonary function [FEV1, FVC, DLCO], diagnosis, clinical staging), pathological data (pathological stage, margin status, lymphovascular invasion, pleural visceral invasion) and operative data (operative time, timing of surgery, morbidity and mortality including post-operative complications and major complications) will be collected.

*\*Post-operative complications:* recurrent pneumothorax, subcutaneous emphysema, prolonged air leak, pneumonia, pulmonary embolism, atrial fibrillation, bleeding, uncontrolled pain, chest tube reinsertion, wound infection, pleural empyema.

Complications will be scored using the Ottawa Thoracic Morbidity and Mortality classification system (15); <https://ottawatmm.org/>.

Clinical and pathological staging will be performed according to AJCC TNM 8th edition.

Specific research data, such as admission/discharge/emergency visit/readmission dates and secondary outcomes data, will be collected in a password-protected document behind the firewall of the MUHC. Only principal investigators and members of the research team will have access to the password.

Descriptive and observational sample analyses will be performed using proportions for categorical variables, means with standard deviations for normally distributed variables and medians with interquartile ranges (IQRs) for skewed distribution variables.

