## 6.6 Stop Criteria

This pilot study will be halted if any of following criteria is met:

- >15% Grade 3 or 4 complications
- Any Grade 5 complications
- >10% readmission rate after 10 patients is discharged on same day

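### Section 2.0 predicts adverse events no more frequent than on the 2-day pathway, but the protocol fixes one arm of 20, descriptive analysis and no comparator, rate or margin

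*Protocol*

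**What the plan says.** The hypothesis in Protocol 2.0 has two parts. The first is that same-day discharge is safe and feasible. The second is that it "will not result in a higher rate of adverse events as compared to patients on a same-day admission pathway" with a 2-day expected stay. The second part is a directional comparison with a named type of patient.

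The rest of the protocol is non-comparative:

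- **Aim (3.0):** "The aim of this phase I study is to evaluate the safety and feasibility of same-day discharge", with no comparator.
- **Size (4.0):** "This trial will be enrolling 20 participants".
- **Design (5.1):** "Study allocation: N/A, single-arm study".
- **Adverse-event outcome (5.4):** "Proportion of participants experiencing complications related to surgery (classified per type of complication"), that is, a proportion of the trial's own participants.
- **Analysis (5.5):** "Descriptive and observational sample analyses will be performed using proportions for categorical variables".

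Two sets of safety limits do appear. In section 3.0, the passage beginning "This pilot study design will be deemed feasible for larger investigations if" requires, among other things, that no serious adverse event raises concern about the pathway. Section 6.6 halts the study for more than "15% Grade 3 or 4 complications", for any Grade 5 complication, or for a readmission rate above 10% once 10 patients have gone home the same day.

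The background (1.0) gives post-operative day 2 as the current discharge target but attaches no adverse-event rate to it. It also reports 8.3% major complications in a retrospective 10-year VATS lobectomy cohort, reviewed to assess a 23-hour pathway. That figure is not linked to the hypothesis.

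**The concern.** A claim that one rate is not higher than another needs the other rate, a source for it, and some statement of how much excess would be tolerated. The protocol supplies none of these and fixes a design that produces only one proportion.

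Adverse event rate is the first of the four primary outcomes, so readers will set the result against the hypothesis. A low count in 20 participants could then be reported as confirming that same-day discharge carries no more complications than the 2-day pathway. The study is meant to inform larger investigations and wider use, so that statement could travel further than its evidence allows.

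**Working it through.** **Is a comparator defined anywhere?** There are three candidates:

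1. *The day-2 pathway in 1.0.* A discharge target is given, but no complication rate.
2. *The 8.3% in 1.0.* This covers major complications only, after VATS lobectomy. The trial's outcome covers every listed surgical complication, and segmentectomy and wedge resection are also eligible (4.1). Outcome and population both differ, and the figure is not named as a benchmark.
3. *The limits in 3.0 and 6.6.* These are absolute and not tied to performance on the 2-day pathway. Meeting them may support a statement that the pathway is acceptable, but not that its rate is no higher than another pathway's.

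**The planned number.** The protocol gives 20 without alpha, power, reference rate or margin, so there is no calculation to reproduce. That is not a fault in a pilot. The question is what 20 can say about the clause.

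**Precision at n = 20** (exact Clopper-Pearson, two-sided 95%). For zero events the upper limit is 1 − 0.025^(1/n):

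| Events | Observed | 95% interval |
|---|---|---|
| 0/20 | 0% | 0 to 16.8% |
| 1/20 | 5% | 0.1% to 24.9% |
| 3/20 | 15% | 3.2% to 37.9% |

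For scale, 16.84 / 8.3 = 2.03, so even a perfect result is compatible with about double the only observed complication rate in the document.

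**Zero-event sample size for an upper limit below 8.3%.** ln(0.025) / ln(1 − 0.083) = 42.57, so 43 participants. Check: 0/42 gives 8.4% and 0/43 gives 8.2%.

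**Can 20 participants detect a worse rate?** Take 8.3% as an assumed fixed reference. An exact one-sided 5% test rejects at 5 or more events (actual level 0.021). If the true rate were doubled to 16.6%, power is 23%.

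**Could 20 show non-inferiority to a fixed 8.3%?** The assumptions are mine: true rate equal to the reference, and the upper limit of the two-sided 95% interval must fall below reference plus margin.

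- *5 points (limit 13.3%):* even 0/20, at 16.8%, fails, so the chance is 0%.
- *10 or 15 points (limits 18.3% and 23.3%):* only 0/20 succeeds, because 1/20 reaches 24.9%. The chance is 0.917^20 = 17.7%.

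**Size needed if the comparison were kept.** With one-sided alpha 0.025, 80% power and equal true rates, a single arm against a fixed reference needs n = p(1 − p)(1.960 + 0.842)² / m². With p = 0.083, the numerator is 0.0761 × 7.849 = 0.597. Margins of 5, 10 and 15 points then give 239, 60 and 27 participants. A concurrent control needs about 478, 120 and 54 per arm.

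**Does the Grade 3 or 4 stop limit fill the gap?** 15% of 20 is 3. Three events do not exceed the limit, yet their interval reaches 37.9%. Staying within the limit is therefore not evidence about a rate relative to the 2-day pathway.

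**The case against.** The best case for the protocol is that section 2.0 states an expectation, not a test. It gives no null hypothesis or alpha, and no planned decision rests on the clause. A historical comparison would fit its wording, the clinical data come from the TSQIC system, whose forms record complication, grade and readmission, and a statistical analysis plan not seen here might name a reference cohort.

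Some of this stands. The feasibility decision and halting rules are unaffected, and the protocol does not itself announce a comparative report. The claim that the clause cannot be tested must be limited to what the protocol fixes. But a later plan could supply a cohort, a rate and a margin; it could not make 20 participants informative about a rate being no higher. The clause would still be out of line with the aim in 3.0.

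The use of 8.3% can also be challenged, because it is a different outcome in a different population. That is right, and it serves only as a scale; the intervals do not depend on it. Likewise, the 43 is the number needed to place the whole interval below the reference, which is stricter than non-inferiority with a margin. At a true rate of 8.3%, 0/43 would occur only about 2% of the time (0.917^43 = 0.024). It should be read as an illustration of precision, not as a proposed sample size.

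Finally, the clause could be kept by naming a 2-day cohort with the same adverse-event definition and calling the comparison descriptive. That would be coherent, but it would still not support the directional statement at this size.

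**Conclusion.** The concern holds. The comparative half of the hypothesis cannot be tested on what the protocol fixes, and it does not match the stated aim. The intervals rest only on n = 20 and the exact binomial method. The ratio of 2.03, the 43, the power and the non-inferiority figures also rest on treating 8.3% as a reference, which the protocol does not do. The non-inferiority and sample-size figures further assume the margins, alpha and power shown.

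The consequence is limited to the safety conclusion on adverse events. It should be corrected, but it does not undermine the pilot's feasibility purpose.

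**What to change.** In section 2.0, end the sentence after its claim of safety and feasibility and delete the comparative clause that follows, so that the hypothesis matches the aim in 3.0. Add one sentence stating that the trial will not be used to conclude that adverse events are no more frequent than on the 2-day pathway. Optionally, say in 5.5 that the adverse-event proportion will be reported with an exact 95% interval, so that a low count is read with its uncertainty.

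The cost is one clause deleted and one sentence added. Sample size, data collection, feasibility criteria and stop criteria do not change. The only loss is a more modest safety claim.

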### **3.0 OBJECTIVES AND PURPOSE**

The aim of this phase I study is to evaluate the safety and feasibility of same-day discharge in participants undergoing anatomical lung resection (segmentectomy or lobectomy) or wedge resection by VATS with an ERP.

#### **Primary Outcomes**

1. Adverse event rate\*
2. Same-day discharge rate
3. Readmission rate
4. Rate of presentation to the emergency room after surgery

#### **Secondary Outcomes**

1. Quality of life
2. Duration of indwelling chest tube catheter
3. Rate of screen failure
4. Percent of eligible participants consented
5. Pathway adherence rate

*\*Post-operative complications:* recurrent pneumothorax, subcutaneous emphysema, prolonged air leak, pneumonia, pulmonary embolism, atrial fibrillation, bleeding, uncontrolled pain, chest tube reinsertion, wound infection, pleural empyema.

Postoperative complications will be classified according to the Ottawa Thoracic Surgery Mortality and Morbidity classification (15).

#### **Feasibility of the Pilot Study**

This pilot study design will be deemed feasible for larger investigations if:

1. The sample population size can be achieved
2. Greater than fifty per cent (>50%) of consented participants are able to continue with same-day discharge post-operatively
3. There are no Serious Adverse Events (SAE) raising concerns about the safety of this ERP

### **4.0 PARTICIPANTS**

This trial will be enrolling 20 participants from the Montreal General Hospital (MGH) at McGill University who are scheduled for an elective anatomical lung or wedge resection with suspected or confirmed pulmonary malignancy. When 20 participants are successfully consented the trial will close to accrual.

#### **4.1 Inclusion criteria**

- Signed or verbal informed consent by participant
- Male and female adults, age 18 and above
- Clinical stage I-II lung cancer (suspected, proven, unproven), or secondary pulmonary malignancy
- BMI < 35
- ECOG 0-1
- Eligible for surgery and lung cancer resection (FEV1 > 60%, DLCO > 60%)

- Elective VATS anatomic resection (segmentectomy or lobectomy), or wedge resection
- Capable caregiver for discharge home

#### **4.2 Exclusion criteria**

- Clinical stage III lung cancer
- Surgery requiring pneumonectomy
- Neoadjuvant therapy
- Active pregnancy or breastfeeding
- History of chronic pain syndromes
- History of chronic opioid use
- Concomitant major surgery indicated with current admission to hospital
- Intraoperative complication including conversion to thoracotomy, major bleeding requiring blood transfusion, extensive adhesiolysis, injury to mediastinal structures, airway injury, nerve injury (phrenic, recurrent)
- Need for epidural or patient-controlled intravenous analgesia
- Need for urinary catheter

### **5.0 DESIGN, METHODOLOGY AND ANALYSIS**

#### **5.1 Study Design**

- Study phase and type: Phase I, prospective observational pilot study
- Study blinding: Open-label
- Study allocation: N/A, single-arm study
- Study setting: Single center, Division of Upper Gastrointestinal and Thoracic Surgery at McGill University Health Centre (Montreal General Hospital)
- Research intervention: Enhanced recovery pathway (ERP) for VATS anatomical lung resection or wedge resection for same-day discharge from hospital
- Estimated enrolment period: September 2022 to September 2023
- Estimated duration of trial: Up to 1 year from first participant enrolled with verbal or signed informed consent to last study-related participant follow-up.
- Estimated duration of trial per participant involvement: From day of consent, to surgery, through follow-up within trial terms (for 4-6 weeks) for a total of approximately 2-3 months. Further follow-up according to usual treatment plan / lung cancer follow-up.

#### **5.2 Participant accrual**

- Estimated enrolment: 20 participants
- Surgeons:
  - [name]
  - [name]
  - [name]
  - [name]
- Study estimated start date: October 2022
- Study estimated completion date: October 2023

#### **5.3 Description of procedures**

SOC - Standard of care; RP – Research procedure

**(a) Pre-operative ERP:**

- Participant education: Tailored preoperative education protocol with information booklet that includes daily goals. [SOC]
- Participant education: Addendum to the information booklet “VATS Guide Addendum” with specifics regarding this research protocol. [RP]
- Participants will be booked as first case of the day. [RP]
- All standard COVID-19 mitigation strategies for thoracic surgery patients will be employed. [SOC]
- Proposed perioperative anesthesia care pathway consensus [See Appendix 1 for more details]. [SOC and RP]
  - All participants will be booked as the first case of the day to allow for a prolonged PACU stay, if needed. [RP]

**(b) Intraoperative ERP:**

- Proposed perioperative anesthesia care pathway consensus [See Appendix 1 for more details]. [SOC and RP]
- Extubation: In the operating room. [SOC]

**(c) Lung resection:** Patients will be placed under General Anesthesia and intubated with a double-lumen endotracheal tube. Patient will be rotated in lateral decubitus so as to elevate the surgical side (16). Standard sterilization and draping will be performed. A 3-5 cm incision will be performed in the fifth or fourth intercostal space and a 1cm incision in the eighth intercostal space. Some surgeons might choose to place a third access port that is 1-3 cm. The pleural cavity will be inspected and the site of tumor, identified. A segmentectomy or lobectomy will be performed in standard protocol. A 20F or 24F tube will be advanced to the thoracic apex and connected to Mini-Atrium dry seal drainage system (Mini-Atrium 500, Atrium, USA). Skin incisions will be closed in standard fashion. The procedures will be performed by staff surgeons from the Division of Upper Gastrointestinal and Thoracic Surgery. [SOC]

**(d) Post-operative ERP:**

- Proposed perioperative anesthesia care pathway [See Appendix 1 for more details]. [SOC]
- Urinary catheter: None, avoid. [SOC]
- Chest tube: Will be connected to a small portable dry seal drainage system (Mini-Atrium 500, Atrium, USA) with which the participants will be discharged. Chest tube will be removed upon the absence of an air-leak and a drainage of less than 800 ml of non-bloody, non-chylous fluid. [Note: Chest tube insertion is SOC, and patients can be discharged with or without tube if they fit removal criteria. Usually, if they are discharged home with the tube, they are seen between post-operative days 5 and 7 in follow-up and removal of chest tube. As part of RP, because participants will be discharged on the same day as surgery, they will all keep the tube and been seen on post-operative day 2 or no later than day POD 7.
- Short-term follow-up: Participants will be seen on post-operative day (POD) 2, and on POD 5 if the chest tube was not removed on POD 2 after surgery. Upon arrival in the outpatient clinic, the participant’s chest tube will be clamped and a chest x-ray will be performed 2 hours later. Moreover, participants will be called daily until chest tube removal or POD 5. Further follow-up will be tailored to participants’ needs. [RP]

**(e) Criteria for safe discharge on the day of surgery [SOC]:**

- Pain well controlled (VAS <3 at rest and <5 when moving)

- Non-bloody chest tube drainage quality, of no more than 100 cc/h over last 4 hours before planned discharge
- No subcutaneous emphysema, clinically and on post-operative x-ray
- Participant independently ambulating to bathroom
- No oxygen requirement and oxygen saturation (SpO2) > 92% on room air at rest
- Stable vital signs (match vitals before surgery) and no documented perioperative tachyarrhythmia
- Dry dressings for the last 4 hours prior to planned discharge
- Participant awake, oriented and cooperative (Glasgow Coma Scale (GCS) 15)
- Bedside swallowing assessment performed by surgeon or thoracic surgery fellow; participant must be able to drink clear liquids without clinical signs of aspiration
- Capable caregiver for discharge home

**(f) Quality of life:**

Quality of life will be assessed using the Functional Assessment of Cancer Therapy - Lung (FACT-L) and the Edmonton Symptom Assessment System (ESAS) questionnaires at the following time points [RP]:

- At the time of consent
- On the day of surgery
- After removal of the chest tube
- 30 days after surgery

## 5.4 Description of outcomes

### Primary Outcomes

1. Adverse event rate: Proportion of participants experiencing complications related to surgery (classified per type of complication).
2. Same-day discharge rate: Proportion of participants enrolled in the trial that go home on the day of the surgery.
3. Readmission rate: Proportion of participants requiring hospitalization due to complications or conditions related to the surgery.
4. Rate of presentation to the emergency room after surgery: Proportion of participants presenting to the emergency room due to complications or conditions related to surgery.

